8. SAFETY REPORTING

Adverse events and serious adverse events will be captured and reported in accordance with the main CRESCENDO study ([Section 10](#)). Since Investigators and the Sponsor will be blinded to the results of these laboratory tests, abnormal results will not be reportable as adverse events.

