independent statistician will be provided with the randomization code list, as well as with regular database transfers. He/she will prepare pro-forma tables, listings, and a report for submission to the DMC. Safety data will include serious adverse events (SAEs), outcome events, local laboratory values, plus other adverse events (AEs) as requested by the DMC. Demography, treatment and trial status data will be presented as requested by the DMC. The report will be based on current data, whether clean or not, and whether adjudicated or not. Although efficacy data will be provided, DMC review of these data does not constitute a formal interim analysis of efficacy, and any analyses of these data will not, in and of themselves, be used for stopping the trial.

National Leadership

In most countries, a National Coordinator will be named. The National Coordinators will be given the following responsibilities:

- Assist the Sponsor in identifying clinical centers, whenever necessary,
- Support the Sponsor for local Investigators' meetings,
- Maintain close contacts with clinical centers,
- Provide scientific and operational support locally, in liaison with the Sponsor and C5.

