9.2 Safety

Safety evaluation will rely on capturing all AEs reported (including neurological and psychiatric AEs based on clinically relevant results of scripted questions asked at each follow-up visit and phone call and on physical examination findings), on vital signs

(supine heart rate and blood pressure) obtained at one, three and six month visits, then at every 6-month visit and at the final visit, and on physical examination and hematology (Hb, Ht, WBC-diff, platelets), and biochemistry (ALT, AST, ALP, creatinine) values obtained at 6-month visits and at the final visit.

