14. SUBSTUDIES

There will be a Metabolic Substudy conducted in selected sites, encompassing approximately 3000 patients. This substudy will assess rimonabant's effects on fasting plasma glucose, insulin, HbA1c, triglyceride, HDL-cholesterol, and LDL-cholesterol levels compared to placebo, in a subset of CRESCENDO patients. Samples will be obtained at baseline and every six months thereafter, and at the End of Study visit. This study will be the subject of a separate protocol ([Appendix 9](#)) and informed consent.

Other substudies of high scientific merit will be conducted based on the recommendation of the Executive Committee. Substudies planned include a Biomarker Substudy and a Genomics Substudy. These studies will be the subject of separate protocols ([Appendix 10](#) and [Appendix 11](#)) and informed consents.

The analysis and reporting of the substudies will be totally separate from the main study.

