3. STUDY DESIGN

Patients randomized in the multinational, multicenter, double-blind, placebo-controlled parallel group CRESCENDO study at selected sites will be asked to participate in this substudy. Once written informed consent is obtained, patients will have blood drawn, after an overnight fast, at baseline, at every 6-month visit, and at the end of study visit. Blood samples will be analyzed at a Central Laboratory, and the Investigators, patients, and Sponsor personnel will be blinded to the results.

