4. SELECTION OF PATIENTS

Sites selected to participate in this substudy will have IRB/EC approval for the main CRESCENDO study and for this substudy and separate informed consent. All subjects must meet eligibility criteria for the main CRESCENDO study, must give written informed consent for that study, and must also give written informed consent for this substudy. Approximately 3000 patients will be expected to participate in this substudy. There are no separate inclusion or exclusion criteria for this substudy, besides the requirement for written informed consent. Patients who have consented to participate in the main study but refuse participation in this substudy will be allowed to continue in the main study.

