5. STUDY PROCEDURES

After an overnight fast, patients will have blood samples drawn for HDL-cholesterol, LDL-cholesterol, triglyceride, plasma glucose, insulin, and HbA1c measurements at baseline, at every 6-month visit, and at the end of study visit. An additional blood sample will be drawn for other metabolic testing that may become indicated. Blood samples will be processed at the site in accordance with directions provided by the Central Laboratory, and shipped to the Central Laboratory facility for analysis. The results of these analyses will be maintained by the Central Laboratory, and the results, coded by patient's initials,

gender, and date of birth, patient's study number, and date blood sample was obtained, will be sent to the Sponsor for loading into the study database. The Investigators and the patients will be blinded to the results.

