7. PRIMARY STATISTICAL ANALYSIS

Changes in fasting HDL-cholesterol, fasting LDL-cholesterol, fasting triglyceride, fasting plasma glucose, fasting insulin, and fasting HbA1c levels at each point in time from baseline will be analyzed and the results compared between the rimonabant and placebo groups, using an analysis of covariance (ANCOVA), with the baseline value as covariate, with a significance level of 0.05.

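### Appendix 9 withholds every Central Laboratory glucose, HbA1c and lipid result from the treating investigator, with no exception for critical values

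*Protocol*

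**What the plan says.** Appendix 9, section 4 sets the size: "Approximately 3000 patients will be expected to participate in this substudy". Section 5 lists HDL- and LDL-cholesterol, triglycerides, plasma glucose, insulin and HbA1c, drawn fasting at baseline, at each 6-month visit and at the end of study.

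Section 3 states that "the Investigators, patients, and Sponsor personnel will be blinded to the results". Section 5 sends the results to the Sponsor for loading into the study database and says again: "The Investigators and the patients will be blinded to the results". Section 8 keeps the main-study reporting of adverse events (AEs) and serious adverse events (SAEs), then adds: "Since Investigators and the Sponsor will be blinded to the results of these laboratory tests, abnormal results will not be reportable as adverse events". None of these sections names an alert limit, a critical-value notice or an unblinded reviewer for individual results.

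In the main study, Section 9.2 limits scheduled chemistry to "biochemistry (ALT, AST, ALP, creatinine) values obtained at 6-month visits and at the final visit". The flowchart in Section 1.1 agrees. Section 6.4 describes what the DMC receives: "Safety data will include serious adverse events (SAEs), outcome events, local laboratory values", plus other adverse events on request. Section 14 says of the substudies: "The analysis and reporting of the substudies will be totally separate from the main study".

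**The concern.** The protocol imposes a rule here; this is not a detail left to another document. It withholds results that can be dangerous in themselves from the one person able to act on them. The population makes this relevant: under Section 7.2, type 2 diabetes, raised fasting glucose and raised triglycerides are all qualifying conditions.

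The rule also fits poorly with the protocol's other safety provisions. Section 10.1 treats a laboratory abnormality as an AE when, among other things, it needs corrective treatment or meets a seriousness criterion. Its example of an asymptomatic ALT rise above 10 times the upper limit accepts that a laboratory value alone can be medically important. Section 8.9.2 wants diabetes and dyslipidemia treated once the need is recognised, but the substudy result that could reveal the need is withheld.

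At stake is the safety of individual substudy patients. The trial's inference is not at stake.

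**Working it through.** The protocol states no figure on this point, so there is none to reproduce. The check has two parts.

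**1. Routes by which a critical substudy value could reach someone**

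| Route | Source | Reaches the treating investigator for that patient? |
|---|---|---|
| Central Laboratory result returned to site | Appendix 9, sections 3 and 5 | No, blinded |
| AE report of the abnormal value | Appendix 9, section 8 | No, declared non-reportable |
| Scheduled main-study chemistry | Sections 1.1 and 9.2 | No, these analytes are not included |
| DMC review | Section 6.4, Appendix 5 | No, but aggregate review is possible |
| Unscheduled local testing | Section 8.9.2 | Yes, if someone orders it |
| Symptoms leading to a clinical AE or SAE | Appendix 9, section 8 | Yes, after the patient becomes ill |

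The last two routes do not depend on the substudy measurement. As the text stands, no stated route carries the measured value itself to the treating investigator.

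**2. How many results are covered**

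Inputs: 3,000 patients (Appendix 9, section 4); follow-up of 33 to 50 months from 17 months of recruitment and a 50-month study (Sections 6.2 and 13.2); draws at baseline, every 6 months and at study end (Appendix 9, section 5). Assumptions: uniform recruitment, and no death, withdrawal or missed draw.

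Panels per patient = 1 (baseline) + floor(T/6) + 1 (final), with T the follow-up in months:

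- T from 33 to 36 (3 of 17 months): floor = 5, so 7 panels
- T from 36 to 42 (6 of 17): floor = 6, so 8 panels
- T from 42 to 48 (6 of 17): floor = 7, so 9 panels
- T from 48 to 50 (2 of 17): floor = 8, so 10 panels

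Mean = (3×5 + 6×6 + 6×7 + 2×8)/17 + 2 = 109/17 + 2 = 8.41.

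Total = 3,000 × 8.41, or about 25,200 panels. The bounds are 3,000 × 7 = 21,000 and 3,000 × 10 = 30,000. Dropout would lower these figures.

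This counts blinded panels. It does not count critical values, for which the documents give no rate.

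**The case against.** **The laboratory manual or substudy consent may already provide alerts.** That is possible, and neither document is available here. If alerts exist, however, they conflict with blinding and reporting text in Appendix 9 that admits no exception, and that text still needs correcting.

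**Section 8 may only record that an unseen value cannot be reported.** The sentence does give blinding as its reason, so a released or locally measured value arguably falls back under Section 10.1. This is a fair reading. It does not close the gap, because nothing in Appendix 9 releases any value.

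**The blinding has a purpose.** Section 8.2 says no planned biological test could unblind treatment, and Section 4.2 reports that rimonabant lowers triglycerides, raises HDL-cholesterol and lowers glucose in diabetics. Routine return of results could hint at allocation. This objection stands and is why routine results should stay blinded.

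**Substudy patients lose nothing relative to the others.** The roughly 14,000 patients outside the substudy also have no scheduled glucose or lipid test, and all receive guideline-based local care under Section 8.9.2. This is true. The difference is that in the substudy the value has been measured and is held in the database.

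A reader might infer that nobody responsible for safety could ever see these data. The documents do not support that. Results enter the study database, the DMC's statistician receives database transfers (Section 6.4, Appendix 5), and the DMC may request any analysis, unblinded if it wishes. Section 14 separates substudy analysis and reporting but does not bar DMC access. What is missing is a patient-level alert.

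A reader might also want a count of patients endangered. Assumed rates of 1 in 10,000 and 5 in 1,000 panels would give about 3 and 126 critical panels (25,235 × 0.0001 and 25,235 × 0.005). That fifty-fold spread comes entirely from the assumption and carries no evidential weight.

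**Conclusion.** The point holds as a patient-safety gap in the substudy. About 3,000 patients and about 25,000 panels (21,000 to 30,000 before dropout) fall under a rule that blinds the investigator to every result and makes abnormal results non-reportable, with no exception for critical values. No main-study test covers the same analytes after entry. How many patients would be affected is unknown.

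The conclusion rests on the protocol text alone. An alert procedure elsewhere would reduce the practical risk but leave the conflicting wording in place. The gap is limited to Central Laboratory results: local testing and treatment are free, and clinical AEs and SAEs are still captured. It would be wrong to infer a threat to the main result, since the primary endpoint analysis, stated power and alpha are not materially affected. This is a cheap improvement that the sponsor should make.

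**What to change.** Amend Appendix 9, sections 3, 5 and 8:

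- Keep routine results blinded, but have the Central Laboratory notify the investigator of any value beyond critical limits fixed in advance, for example extreme glucose or triglycerides. The sponsor should choose the limits.
- Assess released values under the laboratory criteria of Section 10.1, and confine the non-reportable sentence in section 8 to unreleased values.
- If the laboratory manual already contains such alerts, cross-refer to it and remove the conflicting blanket wording.

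The cost is about one paragraph, with matching text in the laboratory manual and substudy consent. There are two downsides. Extra treatment after an alert, possibly more often on placebo, could slightly narrow the substudy comparison made "using an analysis of covariance (ANCOVA), with the baseline value as covariate". Released values could also marginally hint at allocation, or prompt unequal co-treatment, in about 3,000 of the 17,000 main-trial patients. Both argue for limits at truly critical levels. Release at the diabetes diagnostic threshold is not requested, because glucose and HbA1c are substudy outcomes.

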9. ADMINISTRATION

9.1 Informed Consent

A separate informed consent will be obtained from CRESCENDO patients who voluntarily agree to participate in the Metabolic Substudy. The Informed Consent Form reflecting this substudy will be submitted for review and approval to the IRB/EC charged with this responsibility.

9.2 Confidentiality

Blood samples collected for this substudy will be labeled with the patient's initials, gender, and date of birth, study number, site number, and date of collection. Data handling by the Sponsor will be in accordance with that described in the main CRESCENDO protocol ([Section 18](#)), and every effort will be made to protect patient confidentiality. In case the results are published, they will be done so anonymously.

9.3 Institutional Review Board/Ethics Committee

This Metabolic Substudy, the Informed Consent Form for this Metabolic Substudy, and any advertisement for patient recruitment will be submitted for review and approval to the IRB/EC charged with this responsibility.

9.4 Records Retention

Investigators must retain records pertaining to this substudy as described in the main CRESCENDO study protocol ([Section 17.2](#)).

1. INTRODUCTION

Rimonabant is being studied in CRESCENDO to see whether its use is associated with a reduction in myocardial infarction, stroke, or cardiovascular death in abdominally obese patients at increased risk for cardiovascular events. In several other trials, several inflammatory biomarker cytokines have been associated with an increased risk of cardiovascular events. One such marker is C-reactive protein (CRP). In earlier studies, rimonabant use has been shown to be associated with a decrease in CRP. This substudy is being conducted to assess rimonabant's effects on hs-CRP and on other inflammatory markers, including soluble CD40 ligand (sCD40L), interleukin-6 (IL-6), plasminogen activator inhibitor-1 (PAI-1), soluble vascular cellular adhesion molecule-1 (sVCAM-1), P-selectin, and myeloperoxidase, in this patient population at risk for cardiovascular events. In addition, there are other cytokines produced by adipocytes that have been shown to be abnormal in overweight/obese patients, such as adiponectin, resistin, leptin, omentin, osteonectin, and visfatin. These abnormalities may also be associated with insulin resistance, an increase in inflammatory markers, and an increase in atherogenesis and cardiovascular risk. This substudy will also explore whether rimonabant has beneficial effects on these adipocytokines.

2. PRIMARY OBJECTIVE

To evaluate the effect of rimonabant 20 mg OD on hs-CRP, sCD40L, IL-6, PAI-1, sVCAM-1, P-selectin, myeloperoxidase, adiponectin, resistin, leptin, omentin, osteonectin, and visfatin.

3. STUDY DESIGN

Patients randomized in the multinational, multicenter, double-blind, placebo-controlled, parallel group CRESCENDO study at selected sites will be asked to participate in this substudy. Once written informed consent is obtained, patients will have blood drawn at baseline, at every 6-month visit, and at the end of study visit. Blood samples will be analyzed at a Central Laboratory, and the Investigators, patients, and Sponsor personnel will be blinded to the results.

4. SELECTION OF PATIENTS

Sites selected to participate in this substudy will have IRB/EC approval for the main CRESCENDO study and for this substudy and separate informed consent. All subjects must meet eligibility criteria for the main CRESCENDO study, must give written informed consent for that study, and must also give written informed consent for this substudy. Approximately 3000 patients will be expected to participate in this substudy. There are no separate inclusion or exclusion criteria for this substudy, besides the requirement for written informed consent. Patients who have consented to participate in the main study but refuse participation in this substudy will be allowed to continue in the main study.

5. STUDY PROCEDURES

Patients will have blood samples drawn for hs-CRP, sCD40L, IL-6, PAI-1, sVCAM-1, P-selectin, myeloperoxidase, adiponectin, resistin, leptin, omentin, osteonectin, and visfatin measurements at baseline, at every 6-month visit, and at the end of study visit. An additional blood sample will be drawn to provide for any additional testing that may become indicated. Blood samples will be processed at the site in accordance with directions provided by the Central Laboratory, and shipped to the Central Laboratory facility for analysis. The results of these analyses will be maintained by the Central Laboratory, and the results, coded by patient's initials, gender, and date of birth, patient's study number, and date blood sample was obtained, will be sent to the Sponsor for loading into the study database. The Investigators and the patients will be blinded to the results.

6. WITHDRAWAL OF CONSENT

Patients may withdraw consent from participation in this substudy at any time. If they do so, they may continue full participation in the main CRESCENDO study. If they withdraw from study medication, they may continue in this substudy.

7. PRIMARY STATISTICAL ANALYSIS

Changes in hs-CRP, sCD40L, IL-6, PAI-1, sVCAM-1, P-selectin, myeloperoxidase, adiponectin, resistin, leptin, omentin, osteonectin, and visfatin levels at each point in time from baseline will be analyzed and the results compared between the rimonabant and placebo groups, using an analysis of covariance (ANCOVA), with the baseline value as covariate, with a significance level of 0.05.

8. SAFETY REPORTING

Adverse events and serious adverse events will be captured and reported in accordance with the main CRESCENDO study ([Section 10](#)). Since Investigators and the Sponsor will be blinded to the results of these laboratory tests, abnormal results will not be reportable as adverse events.

9. ADMINISTRATION

9.1 Informed Consent

A separate informed consent will be obtained from CRESCENDO patients who voluntarily agree to participate in the Biomarker Substudy. The Informed Consent Form reflecting this substudy will be submitted for review and approval to the IRB/EC charged with this responsibility.

9.2 Confidentiality

Blood samples collected for this substudy will be labeled with the patient's initials, gender, and date of birth, patient's study number, and date of collection. Data handling by the Sponsor will be in accordance with that described in the main CRESCENDO protocol ([Section 18](#)), and every effort will be made to protect patient confidentiality. In case the results are published, they will be done so anonymously.

9.3 Institutional Review Board/Ethics Committee

This Biomarker Substudy, the Informed Consent Form for this Biomarker Substudy, and any advertisement for patient recruitment will be submitted for review and approval to the IRB/EC charged with this responsibility.

1. STUDY OBJECTIVES

Primary Objective:

The primary objective of the CRESCENDO Genomics Blood Sample Substudy is to collect blood samples that may be used for future hypothesis generating and hypothesis testing research from subjects enrolled in CRESCENDO Protocol Study Number EFC5826.

Research that may be conducted on samples collected from this protocol or in combination with samples from other protocols can explore:

- 1) how variations in genes associate with clinical outcomes, eg, drug metabolizing enzyme variants with either pharmacokinetic endpoints or other clinical responses;
- 2) the associations among genetic variation, gene expression, and proteins and clinical conditions, such as obesity or metabolic disorders, and outcomes, such as MI, stroke, or cardiovascular death.

2. STUDY DESIGN

Subjects who have consented to participate in the CRESCENDO study and who voluntarily have given written informed consent for genomic sample collection will have a one-time blood sample drawn at any of the scheduled blood sample collections for clinical laboratory tests during this protocol. The sample will be shipped overnight (room temperature) the day it is collected to a designated central laboratory for processing. The sample will be stored frozen for banking at a Genetic Sample Bank (GSB) for genomic research studies. The sample will be shared with The Cleveland Clinic Foundation (CCF) and sanofi-aventis. These samples will be destroyed no later than 20 years from the date of collection.

3. SELECTION OF SUBJECTS

Genomic blood sample collection will be performed at CRESCENDO sites that permit genomic studies to be conducted in compliance with all applicable laws, rules, and regulations. Subjects enrolled in CRESCENDO Protocol Study Number EFC5826 at sites that have appropriate Institutional Review Board/Ethics Committee approval will be asked to participate voluntarily in the genomic research substudy. Subjects will be asked to read, understand, and sign an informed consent form designed for the purpose of collecting a one-time blood for genomic research. **Subjects will be informed that they will not be excluded from the CRESCENDO study if they do not wish to participate in the Genomic Blood Sample Substudy.**

4. ETHICS

The CRESCENDO Genomics Blood Sample Substudy can only be implemented where consistent with local law and only when the local IRB/Ethics Committee and Clinical Investigator have agreed to allow study subjects to participate in this portion of the study.

5. WITHDRAWAL OF SUBJECT CONSENT

5.1 Withdrawal of Subjects from Genomic Blood Sample Substudy

Subjects have, at any time, the option to withdraw consent for participation from

- 1) Only the Genomic Blood Sample Substudy independent of the CRESCENDO treatment protocol;
OR
- 2) Only the CRESCENDO study drug independent of the Genomic Blood Sample Substudy;
OR
- 3) Both the CRESCENDO clinical treatment and the Genomic Blood Sample Substudy.

Subjects who wish to withdraw their consent from the Genomic Blood Sample Substudy [ie, have their blood/DNA samples destroyed (see Section 5.2)] should contact the Investigator. The Investigator will submit a Sample Withdrawal Form to the GSB. The GSB will notify in writing CCF and sanofi-aventis.

It is possible that subjects may decide to withdraw consent from the CRESCENDO study drug but continue with their consent for the CRESCENDO Genomic Blood Sample Substudy. In such cases, the Investigator should inform subjects that their blood/DNA sample would remain stored at the GSB, CCF, and sanofi-aventis and will remain subject to genomic research.

5..2. Destruction of Blood Sample and Related Material

In the case of subjects who have withdrawn their consent for participation in the Genomic Blood Sample Substudy, the Investigator will send a Sample Withdrawal Form to the GSB. GSB will send a copy of the Sample Withdrawal Form to CCF and sanofi-aventis. CCF and sanofi-aventis, upon receipt of the Sample Withdrawal Form, will destroy all of the remaining blood sample and material obtained from the blood sample. A copy of the genetic sample destruction form is attached to this Appendix. CCF and sanofi-aventis will notify GSB in writing of the sample destruction. After all samples have been destroyed GSB will provide the Investigator with verification of the sample destruction. In the case of samples that have been partially analyzed the

remaining sample will be destroyed but CCF and sanofi-aventis shall be entitled to retain and use any research results obtained prior to the withdrawal of consent.

